
Study Termination/ Individual Study Site Termination
	
The Sponsor may terminate this study prematurely, either in its entirety or at any study site, for reasonable cause provided that written notice is submitted in advance of the intended termination. Advanced notice is not required if the study is stopped due to safety concerns. If the Sponsor terminates the study for safety reasons, the Sponsor will immediately notify the Investigator and subsequently provide written instructions for study termination. If the study has been suspended or terminated, prompt notification will be given to Investigators, IRBs, and regulatory authorities in accordance with regulatory requirements.

Statistical Considerations
	
Efficacy and safety endpoint analysis will be descriptive in nature. Continuous variables will be summarized using number of subjects with mean, standard deviation (SD), median, minimum and maximum. For categorical variables, the number and percentage of subjects in each category will be tabulated.
 
PK and PD parameters will be summarized using descriptive statistics: number of subjects, mean, median, SD, minimum, maximum, and coefficient of variation,

	geometric mean and geometric mean SD. Mean and individual plasma concentration-time profiles will be presented graphically in both linear scale and log-linear scale. The ESA hyporesponder parallel study will be analyzed separately from the main study.
PK Analysis	A population PK analysis will be conducted to describe vadadustat PK and determine the covariates that impact the PK profile (i.e., demographics, laboratory values, concomitant iron, dosing relative to dialysis, etc). PK analysis will be reported separately.
PD Analysis	An exposure-response analysis of vadadustat, EPO and other PD measures will be conducted as deemed appropriate. PD analysis will be reported separately.

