#### **8.4.1 Randomization**

##### Main Study:

Subjects will be randomized to either a vadadustat treatment arm or epoetin alfa treatment arm. Randomization will be stratified by mean weekly epoetin alfa dose calculated over a period of 8 weeks prior to SV2:

- Low epoetin alfa dose group ( $\leq 90$  U/kg/week) or
- High epoetin alfa dose group ( $> 90$  to  $< 300$  U/kg/week)

In the low epoetin alfa dose group, subjects will be randomized in a 3:3:2 ratio to receive either an initial vadadustat daily dose of 450 mg (3 tablets) or 300 mg (2 tablets), or epoetin alfa.

In the high epoetin alfa dose group, subjects will be randomized in a 3:3:3:2 ratio to receive either an initial vadadustat daily dose of 600 mg (4 tablets), 450 mg (3 tablets) or 300 mg (2 tablets), or epoetin alfa.

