### 11.1 Sample Size Estimation

Approximately 95 subjects are planned for enrollment in the Main study with 40 and 55 subjects randomized to the low epoetin alfa dose group and the high epoetin alfa dose group, respectively. Approximately 30 subjects are planned for enrollment in the ESA hyporesponder parallel study.

Sample size reflects the exploratory nature of this study.

Enrollment may be increased by up to 20 additional subjects in the Main study and by up to 30 additional subjects in the ESA hyporesponder parallel study to ensure adequate data is captured for the primary, PK/PD, and safety endpoints.

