### 11.2 Study Analysis Populations

The following analysis populations will be used in this study:

- Randomized population: defined as all randomized subjects. Analyses of this population will be based on the randomized treatment.
- Full Analysis Population (FAS): all subjects in the randomized population who received at least one dose of study drug and had at least one Hb assessment during the primary efficacy evaluation period. Analyses of this population will be based on the randomized treatment.
- Safety Population: all subjects in the randomized population who received at least one dose of study treatment. Analysis of this population will be based on the actual treatment received. Subjects who received in error some vadadustat and some epoetin alfa will be classified by the more frequently received drug.
- Per protocol (PP) population: all randomized subjects who received study drug during the primary evaluation period, had at least one Hb assessment during the primary efficacy evaluation period, received no rescue therapy (with ESA or transfusion) prior to the evaluation period, and had no major protocol deviation affecting the primary endpoint analyses. Major protocol deviations leading to exclusion from the PP population will be specified prior to database lock and recorded in a separate document. Analyses of this population will be based on actual treatment received.

Efficacy analyses will utilize the Randomized, Full Analysis, and PP Populations while safety analyses will utilize the Safety Population.

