### **11.6 Efficacy Analyses**

The primary efficacy endpoint as well as all other secondary endpoints will be summarized using descriptive statistics (means or proportions) by treatment groups and in total, as well as by study visit and/or analysis period as appropriate. Mean values of Hb as well as selected other efficacy parameters will be plotted across study visits/periods by treatment group.

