##### **8.4.5.2 Transition of Vadadustat Once Daily Dosing to TIW Dosing Regimen**

All subjects randomized to vadadustat who complete 12 weeks of once daily dosing regimen **and** who meet all the Week 12 criteria below will be transitioned to a TIW vadadustat dosing regimen.

Week 12 Transition criteria:

- Vadadustat daily dose of 600 mg or lower at Week 12
- Hb within target range of 10.0 to 11.0 g/dL, inclusive, at Week 12 confirmed by central laboratory Hb value from Week 11 (11 weeks of treatment completed)
- No receipt of rescue therapy (ESA or RBC transfusion) for worsening of anemia due to CKD from Baseline/Day 1 to Week 12.
  - ESA or RBC transfusion prior to Week 12 for reasons unrelated to worsening of anemia due to CKD (e.g., surgery, gastrointestinal bleed, or inadvertent administration) is not considered rescue therapy
- No other reason, based on the Investigator's clinical discretion, that would make the subject not suitable for TIW dosing.

Selected subjects who meet Week 12 transition criteria will transition to the TIW vadadustat dosing regimen at the Week 12 visit. Subjects on 150 mg, 300 mg, 450 mg, or 600 mg of vadadustat daily at the Week 12 visit will transition to an initial vadadustat TIW dose one tablet greater (+150 mg), i.e., 300 mg, 450 mg, 600 mg, or 750 mg vadadustat TIW, respectively. Subjects will be instructed to take vadadustat on dialysis days.

After 2 weeks of treatment in the TIW vadadustat dosing regimen (at Week 14), subjects in any vadadustat TIW dosing arms who have a decline in Hb  $\geq 0.5$  g/dL will be eligible for a dose increase by 1 tablet, based on the Investigator's clinical discretion.

Subjects who are not eligible to switch from daily vadadustat to TIW dosing at Week 12 will remain on daily dosing for the remainder of the study.

Subjects on TIW dosing may be converted back to vadadustat once daily dosing at the discretion of the Investigator in the setting of inadequate Hb response. The starting daily dose after the switch from TIW to daily dosing will be based on the Investigator's discretion after review of the subject's clinical status and dosing history, in particular, the daily dose previously administered to the subject prior to the transition to TIW dosing (Week 12). Subjects who switch from vadadustat TIW to daily dosing will continue once daily vadadustat until the end of the Treatment Period.

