### **8.4.9.2 ESA Use**

ESA administration will be allowed when medically necessary at the discretion of the Investigator. In general, ESA will not be administered in subjects with Hb  $\geq 8.5$  g/dL, and ESA will be stopped when Hb  $\geq 9.0$  g/dL. ESA therapy will be administered using an approved ESA and dosing as per the local institution's guidelines and per the approved product label.

While receiving ESA therapy, subjects randomized to vadadustat must temporarily interrupt vadadustat. A minimum interval will be observed prior to restarting vadadustat after the last dose of ESA, and treatment will be resumed after the following intervals:

- 2 days after last dose of epoetin alfa
- 7 days after last dose of darbepoetin alfa
- 14 days after last dose of methoxy polyethylene glycol-epoetin beta

Following ESA administration, vadadustat will be resumed at the same dose as previously used or with one additional tablet (+150 mg) at the discretion of the Investigator.

Reasons for ESA use will be captured in the appropriate CRF.

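### The per-protocol rule excludes rescue only before Week 10, so Hb raised by rescue during Weeks 10 to 12 stays in the per-protocol primary summary

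*Protocol*

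**What the plan says.** Section 5.3.1 defines the primary endpoint as the change from average pretreatment Hb to average Hb over Weeks 10 to 12. The schedule places three Hb visits there (Weeks 10, 11 and 12).

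Section 11.2 names three efficacy populations: Randomized, Full Analysis (FAS) and PP. Only PP has a rescue condition: the subject "received no rescue therapy (with ESA or transfusion) prior to the evaluation period". PP also requires study drug and at least one Hb value in the evaluation period, and no major protocol deviation affecting the primary analysis.

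Rescue is permitted care. Section 8.4.9.1 allows transfusion in either arm and lets study drug continue through it. Section 8.4.9.2 states that "ESA administration will be allowed when medically necessary at the discretion of the Investigator". It requires vadadustat to be interrupted meanwhile, with a restart 2, 7 or 14 days after the last ESA dose, depending on the product.

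Section 8.4.5.2 lists the conditions for moving to three-times-weekly dosing. One is no rescue for worsening anaemia due to CKD from Baseline/Day 1 to Week 12. It adds that "ESA or RBC transfusion prior to Week 12 for reasons unrelated to worsening of anemia due to CKD" does not count as rescue.

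Under Section 11.6 the efficacy endpoints "will be summarized using descriptive statistics (means or proportions) by treatment groups and in total".

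**The concern.** A PP analysis is meant to show Hb on the assigned drug without help from rescue. Here the exclusion closes just as the endpoint opens. A subject rescued in Week 9 is removed. A subject rescued in Week 11 is kept, and the raised Week 12 value is averaged in as if the assigned drug had produced it.

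The protocol also contradicts its own standard. A vadadustat subject rescued for worsening anaemia in Week 11 fails the Section 8.4.5.2 condition for having been managed on daily dosing, yet qualifies for the PP summary of 12 weeks of daily dosing. At stake is the credibility of the PP mean change, and to a lesser extent the PP proportions, in arms of 10 to 15 subjects.

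**Working it through.** **Does another PP condition close the gap?** Three were checked.

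1. *Study drug in the evaluation period.* A transfused subject can meet this because study drug may continue. An ESA-rescued vadadustat subject can meet it through doses taken in the window before rescue, or after restarting. Only a subject with no study drug at all in the window is removed.
2. *No major deviation.* Permitted rescue is not a deviation. Inadvertent ESA during vadadustat is reported as one (Section 8.5.2) and could be caught, but that is a different event.
3. *At least one Hb value in the window.* This removes nobody because of rescue.

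So the gap is real on the text.

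**Arm sizes.** The plan has no power calculation to reproduce: "Sample size reflects the exploratory nature of this study". The allocation arithmetic agrees with the planned numbers.

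- Low-dose group: "In the low epoetin alfa dose group, subjects will be randomized in a 3:3:2 ratio". 40 × 3/8 = 15, 40 × 3/8 = 15, 40 × 2/8 = 10.
- High-dose group: "In the high epoetin alfa dose group, subjects will be randomized in a 3:3:3:2 ratio". 55 × 3/11 = 15 (three arms), 55 × 2/11 = 10.
- Main-study vadadustat pooled: 5 × 15 = 75.

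**Effect on the arm mean.** For *k* subjects rescued in the window, *n* in the arm, an Hb rise *d*, and *v* of the three averaged visits falling after rescue:

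shift = (*k*/*n*) × *d* × (*v*/3)

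The documents give no Hb rise, so *d* = 0.5, 1.0 and 2.0 g/dL is assumed. Rescue between the Week 10 and 11 visits gives *v* = 2; between Weeks 11 and 12 it gives *v* = 1.

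| n | k | d = 0.5 | d = 1.0 | d = 2.0 |
|---|---|---|---|---|
| 10 | 1 | 0.017–0.033 | 0.033–0.067 | 0.067–0.133 |
| 15 | 1 | 0.011–0.022 | 0.022–0.044 | 0.044–0.089 |
| 15 | 3 | 0.033–0.067 | 0.067–0.133 | 0.133–0.267 |
| 75 | 1 | 0.002–0.004 | 0.004–0.009 | 0.009–0.018 |

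Values are g/dL, for *v* = 1 to *v* = 2. Example: (1/15) × 2.0 × (2/3) = 0.089.

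**Effect on a proportion.** One reclassified subject is at most 1/15 = 6.7 points, 1/10 = 10 points, or 1/75 = 1.3 points.

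**How likely is a rescue in the window?** The documents give no rescue rate. As a rough proxy, Section 4.2 reports withdrawal for worsening anaemia over 16 weeks in the earlier haemodialysis study: 0/30, 1/33 and 6/31. Assuming a constant hazard, the two-week risk is 1 − (1 − p)^(2/16).

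- p = 1/33: risk 0.0038. Chance of at least one rescue is 5.6% in 15 subjects and 25% in 75.
- p = 6/31: risk 0.0265. Chance is 33% in 15 and 87% in 75 (about 2 expected). This was a three-times-weekly arm, so it is a high bound for daily dosing.
- p = 0/30: risk 0.

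**After the fix.** With the exclusion run to the end of Week 12, rescue within its definition contributes 0 to the PP mean.

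**The case against.** The strongest reply is that little depends on this. The synopsis says "Efficacy and safety endpoint analysis will be descriptive in nature"; there is no test, margin or decision rule. PP is one of three populations. ESA rescue and transfusion are separate secondary endpoints, and reasons for exclusion are listed by subject, so failures are reported. All of that stands, and it limits severity.

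Four stronger readings might be inferred; the documents do not support them.

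- *That the FAS and Randomized summaries are defective because no rule removes post-rescue Hb or stops it being carried forward.* Such rules can sit in the SAP, which is not shown. Averaging Hb regardless of rescue, with rescue reported separately, is also a legitimate treatment-policy summary.
- *That PP drops failures from one arm only.* Transfusion excludes subjects in either arm. Only the ESA part falls mainly on vadadustat, since an epoetin alfa subject with low Hb can be given more study drug and stay in PP.
- *That the gap necessarily favours vadadustat.* The wording applies to both arms. The direction depends on the difference in rescue rates, which the documents do not give.
- *That two or three of 15 subjects could be wrongly scored in range.* Nothing supports that count. ESA rescue is generally not given at Hb 8.5 g/dL or above and is stopped at 9.0 or above, well short of 10.0, so any reclassification into the target range would come mainly from transfusion. Nor do those start and stop thresholds guarantee a rise of 0.5 g/dL.

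**Conclusion.** The concern holds as a defect in the PP definition. As written, Section 11.2 keeps subjects rescued during Weeks 10 to 12 and lets their post-rescue Hb into the primary summary. That is inconsistent with the window in Section 8.4.5.2.

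The size is about 0.01 to 0.09 g/dL per such subject on the mean of an arm of 15, and up to 6.7 points on a proportion. In the pooled Main-study vadadustat group it is at most about 0.02 g/dL and 1.3 points. These figures rest on the assumed Hb rise and on one or two of three visits following rescue. A subject rescued before the Week 10 blood draw but inside the window would contribute at all three.

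This is a cheap wording correction to a descriptive analysis and does not threaten the trial's conclusions. One limit applies: the Section 11.2 text comes from the first of two protocol versions in the file. The later version is cut off before its Section 11, so whether the wording changed cannot be confirmed. The rescue and transition text is the same in both.

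**What to change.** 1. In Section 11.2, change the PP condition to *no rescue therapy prior to or during the primary evaluation period*. Alternatively, keep the subject and leave Hb values after in-window rescue out of the PP average. That option retains the pre-rescue Hb of a failing subject, but the plan must then say whether the last-observation rule in Section 11.5 fills the gap.
2. Define rescue for PP as Section 8.4.5.2 does, that is, for worsening of anaemia due to CKD, so both rules identify the same subjects. Transfusion for bleeding or surgery would then not exclude a subject; say so explicitly.
3. Report by arm the number excluded from PP for ESA and for transfusion separately, because the ESA part falls mainly on vadadustat.
4. Check the wording of Section 11 in the later protocol version and apply the same change there.

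The cost is one phrase and a derived rescue flag. Reasons for rescue are already captured on the CRF, and rescue use is reviewed at each treatment visit. The downside is a slightly smaller PP set that loses a few more rescued subjects, mainly from the vadadustat arm, which is why the counts in item 3 matter. Clinical management does not change.

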### **11.3 Analysis of Demographic and Pretreatment Variables**

Descriptive statistics will be generated for demographic and pretreatment variables for Randomized Population and other analysis populations which will be defined in detail in the Statistical Analysis Plan.

Medical history terms will be coded using the Medical Dictionary for Regulatory Activities (MedDRA) and summarized by System Organ Class (SOC) and Preferred Term (PT) for each treatment group based on the safety population.

### **11.4 Disposition of Subjects**

The number and percentage of subjects randomized and included in each analysis population will be summarized by treatment and overall. Reasons for excluding subjects from the analysis populations will be presented in a by-subject listing.

The number of randomized subjects who completed the study, discontinued early from study drug, completed or discontinued from the study, and reasons for discontinuation will be summarized by treatment group and overall.

### **11.5 Missing Data**

It is expected that few subjects will discontinue Follow-Up. The reasons for any missing data will be summarized by treatment arm. Missing Hb values will be imputed using last observation carried forward (LOCF).

### **11.6 Efficacy Analyses**

The primary efficacy endpoint as well as all other secondary endpoints will be summarized using descriptive statistics (means or proportions) by treatment groups and in total, as well as by study visit and/or analysis period as appropriate. Mean values of Hb as well as selected other efficacy parameters will be plotted across study visits/periods by treatment group.

### **11.7 Safety Analyses**

Safety analyses will be descriptive in nature.

All AEs will be coded using MedDRA. Treatment-emergent and post-treatment AEs will be summarized by SOC and PT for each treatment group. AEs will also be summarized by their maximum severity.

Summaries will also be provided for the following types of AEs:

- SAEs
- Related AEs, as determined by the Investigator
- AEs leading to early discontinuation of study drug

All Hb related safety endpoints will be tabulated for each treatment groups.

Observed values of continuous and categorical parameters and changes from baseline for continuous parameters to each study visit will be summarized descriptively for vital signs and clinical laboratory results. Graphical displays of selected laboratory parameters will also be provided.

## **11.8 Additional Assessments**

PK and PD parameters will be summarized using descriptive statistics: number of subjects, mean, median, SD, minimum, maximum, and coefficient of variation, geometric mean and geometric mean SD. Mean and individual plasma concentration-time profiles will be presented graphically in both linear scale and log-linear scale.

### **11.8.1 PK Assessments**

A population PK analysis will be conducted to describe vadadustat PK and determine the covariates that impact the PK profile (i.e., demographics, laboratory values, concomitant iron, dosing relative to dialysis, etc.). PK analysis will be reported separately.

### **11.8.2 PD Assessments**

An exposure-response analysis of vadadustat, EPO and other PD measures will be conducted as deemed appropriate. PD analysis will be reported separately.

### **11.8.3 Concomitant Medications**

Prior and concomitant medications will be coded using World Health Organization Drug dictionary. Refer to [Section 8.5](#), Prior and Concomitant Therapy.

### **11.8.4 Biomarkers**

Biomarkers (including, but not limited to, hepcidin and VEGF) will be summarized descriptively at Baseline/Day 1 and by visit post-Baseline/Day 1.

## **12 DATA HANDLING AND RECORD KEEPING**

### **12.1 CRFs/EDC**

This study will utilize an EDC system to manage data collection during this trial. The system is fully Code of Federal Regulations 21 part 11 compliant. An EDC system contains certain functionality including, but not limited to, a graphical user interface to help facilitate data entry, a data validation element to check user data, and a reporting function to assist with the review and analysis of data. CRFs available through this system are required and will be completed for each randomized subject.

Any form of data from the electronic system are the sole property of the Sponsor and will not be made available in any form to third parties, except for authorized representatives of the Sponsor or appropriate regulatory authorities, without written permission from the Sponsor.

The Investigator has ultimate responsibility for the accuracy, authenticity, and timely collection and reporting of all clinical, safety, and laboratory data entered in the EDC or any other data collection forms. The CRFs will be signed electronically by the Investigator to attest that the data contained on the CRFs is true.

In most cases, the source documents are contained in the subject's chart at the hospital or the physician's office. In these cases, data collected on the CRFs will match the data in those charts.

### **12.2 Record Retention**

To enable evaluations and/or audits from regulatory authorities or the Sponsor, the Investigator agrees to keep records, including the identity of all participating subjects (sufficient information to link records, e.g., CRFs and hospital records), all original signed informed consent forms, copies of all CRFs, SAE forms, source documents, detailed records of drug disposition, and adequate documentation of relevant correspondence (e.g., letters, meeting minutes, and telephone calls reports). The records will be retained by the Investigator according to the International Council for Harmonisation of Technical Requirements for Pharmaceuticals for Human Use (ICH), local regulations, or as specified in the Clinical Study Agreement, whichever is longer.

If the Investigator becomes unable for any reason to continue to retain study records for the required period (e.g., retirement and relocation), the Sponsor will be prospectively notified. The study records will be transferred to a designee acceptable to the Sponsor, such as another Investigator, another institution, or to the Sponsor. The Investigator will obtain Sponsor's written permission before disposing of any records, even if retention requirements have been met.

